## Statistical Analysis Plan

## Open-Label Extension Study–Eosinophilic Asthma

## Study C38072-AS-30066

Term	Code	Level	List from Panel on Opportunistic Infections in HIV-Infected Adults and Adolescents	If LLT- under which PT
Cervix carcinoma stage IV	10008348	PT	Cervical cancer invasive	
Coccidioides infections	10009824	HLT	Coccidioidomycosis, disseminated or extrapulmonary	
Cryptococcosis	10011490	PT	Cryptococcosis, extrapulmonary	
Cryptococcal fungaemia	10067112	PT	Cryptococcosis, extrapulmonary	
Cryptococcal cutaneous infection	10054216	PT	Cryptococcosis, extrapulmonary	
Disseminated cryptococcosis	10013439	PT	Cryptococcosis, extrapulmonary	
Gastroenteritis cryptococcal	10011485	PT	Cryptococcosis, extrapulmonary	
Meningitis cryptococcal	10027209	PT	Cryptococcosis, extrapulmonary	
Neurocryptococcosis	10068368	PT	Cryptococcosis, extrapulmonary	
Cryptosporidia infections	10011499	HLT	Cryptosporidiosis infection, chronic intestinal (> 1 month duration)	
Cytomegalovirus chorioretinitis	10048843	PT	Cytomegalovirus disease (other than liver, spleen, or nodes)	
Cytomegalovirus colitis	10048983	PT	Cytomegalovirus disease (other than liver, spleen, or nodes)	
Cytomegalovirus duodenitis	10049014	PT	Cytomegalovirus disease (other than liver, spleen, or nodes)	
Cytomegalovirus enteritis	10049074	PT	Cytomegalovirus disease (other than liver, spleen, or nodes)	
Cytomegalovirus enterocolitis	10049015	PT	Cytomegalovirus disease (other than liver, spleen, or nodes)	
Cytomegalovirus gastritis	10049016	PT	Cytomegalovirus disease (other than liver, spleen, or nodes)	
Cytomegalovirus gastroenteritis	10051349	PT	Cytomegalovirus disease (other than liver, spleen, or nodes)	
Cytomegalovirus gastrointestinal infection	10052817	PT	Cytomegalovirus disease (other than liver, spleen, or nodes)	
Cytomegalovirus gastrointestinal ulcer	10075619	PT	Cytomegalovirus disease (other than liver, spleen, or nodes)	
Cytomegalovirus nephritis	10079095	PT	Cytomegalovirus disease (other than liver, spleen, or nodes)	

Statistical Analysis Plan

Open-Label Extension Study–Eosinophilic Asthma

Study C38072-AS-30066

Term	Code	Level	List from Panel on Opportunistic Infections in HIV-Infected Adults and Adolescents	If LLT- under which PT
Cytomegalovirus mucocutaneous ulcer	10065036	PT	Cytomegalovirus disease (other than liver, spleen, or nodes)	
Cytomegalovirus myelomeningoencephalitis	10065621	PT	Cytomegalovirus disease (other than liver, spleen, or nodes)	
Cytomegalovirus myocarditis	10056261	PT	Cytomegalovirus disease (other than liver, spleen, or nodes)	
Cytomegalovirus oesophagitis	10049018	PT	Cytomegalovirus disease (other than liver, spleen, or nodes)	
Cytomegalovirus pancreatitis	10049566	PT	Cytomegalovirus disease (other than liver, spleen, or nodes)	
Cytomegalovirus pericarditis	10056721	PT	Cytomegalovirus disease (other than liver, spleen, or nodes)	
Cytomegalovirus urinary tract infection	10051350	PT	Cytomegalovirus disease (other than liver, spleen, or nodes)	
Disseminated cytomegaloviral infection	10049075	PT	Cytomegalovirus disease (other than liver, spleen, or nodes)	
Encephalitis cytomegalovirus	10014586	PT	Cytomegalovirus disease (other than liver, spleen, or nodes)	
Pneumonia cytomegaloviral	10035676	PT	Cytomegalovirus disease (other than liver, spleen, or nodes)	
Hepatitis B	10019731	PT	Hepatitis B	
Acute hepatitis B	10059193	PT	Hepatitis B	
Chronic hepatitis B	10008910	PT	Hepatitis B	
Hepatitis C	10019744	PT	Hepatitis C	
Acute hepatitis C	10065051	PT	Hepatitis C	
Chronic hepatitis C	10008912	PT	Hepatitis C	
Herpes simplex skin chronic ulcers	10058426	LLT	Herpes simplex ulcers chronic (>1mo)	Under "Herpes dermatitis" PT
Lower respiratory tract herpes infection	10019948	PT	Herpes simplex bronchitis	
Herpes simplex pneumonia	10065046	PT	Herpes simplex pneumonitis	
Pneumonia herpes viral	10035703	PT	Herpes simplex pneumonitis	

Statistical Analysis Plan

Open-Label Extension Study–Eosinophilic Asthma  
Study C38072-AS-30066

Term	Code	Level	List from Panel on Opportunistic Infections in HIV-Infected Adults and Adolescents	If LLT- under which PT
Herpes simplex oesophagitis	10074242	PT	Herpes simplex oesophagitis	
Herpes oesophagitis	10052330	PT	Herpes simplex oesophagitis	
Shingles	10040555	LLT	Shingles when 2 distinct episodes or more than 1 dermatome	Under "Herpes zoster" PT
Herpes zoster cutaneous disseminated	10074297	PT	Shingles when 2 distinct episodes or more than 1 dermatome	
Herpes zoster disseminated	10065038	PT	Shingles when 2 distinct episodes or more than 1 dermatome	
Histoplasmosis	10020141	PT	Histoplasmosis extrapulmonary	
Histoplasmosis disseminated	10020144	PT	Histoplasmosis disseminated	
Endocarditis histoplasma	10014676	PT	Histoplasmosis disseminated	
Histoplasmosis cutaneous	10049142	PT	Histoplasmosis disseminated	
Meningitis histoplasma	10027243	PT	Histoplasmosis disseminated	
Pericarditis histoplasma	10034489	PT	Histoplasmosis disseminated	
Presumed ocular histoplasmosis syndrome	10063664	PT	Histoplasmosis disseminated	
Retinitis histoplasma	10038912	PT	Histoplasmosis disseminated	
HIV wasting syndrome	10050309	PT	Wasting secondary to HIV	
Human polyomavirus infection	10057366	PT	Human polyomavirus infection	
Immunoblastic lymphoma	10053574	PT	Lymphoma immunoblastic	
Isosporiasis	10023076	PT	Isosporiasis, chronic intestinal (> 1 month's duration)	
Kaposi's sarcomas	10023285	HLT	Kaposi's sarcoma	
Lymphoid interstitial pneumonia	10062997	LLT	Lymphoid interstitial pneumonia	Under " Idiopathic interstitial pneumonia " PT
Listeria infections	10024639	HLT	Listeriosis	
Atypical mycobacterial infections	10003754	HLT	Mycobacterium infections, other species or unidentified species, disseminated or extrapulmonary (eg, M. haemophilum , M. fortuitum , or M. marinum )	
Nocardia infections	10029443	HLT	Nocardiosis	

Term	Code	Level	List from Panel on Opportunistic Infections in HIV-Infected Adults and Adolescents	If LLT- under which PT
Pneumocystis jirovecii infection	10073756	PT	Pneumocystis jirovecii infection	
Pneumocystis jirovecii pneumonia	10073755	PT	Pneumocystis jirovecii infection	
Pneumonia recurrent	10066727	LLT	Pneumonia recurrent	Under "Pneumonia" PT
Polyomavirus-associated nephropathy	10065381	PT	Polyomavirus (JC virus or BK virus)-associated nephropathy (including progressive multifocal leukoencephalopathy)	
JC virus granule cell neuronopathy	10074361	PT	Polyomavirus (JC virus or BK virus)-associated nephropathy (including progressive multifocal leukoencephalopathy)	
Progressive multifocal leukoencephalopathy	10036807	PT	Polyomavirus (JC virus or BK virus)-associated nephropathy (including progressive multifocal leukoencephalopathy)	
Central nervous system lymphoma	10007953	PT	Lymphoma primary of brain	
Respiratory moniliasis	10038705	PT	Candidiasis of bronchi	
Candidiasis of trachea	10064459	PT	Candidiasis of trachea	
Candida pneumonia	10053158	PT	Candidiasis of lungs	
Salmonella sepsis	10058878	PT	Salmonella sepsis	
Salmonella septicemia	10039445	LLT	Salmonella septicemia, recurrent	Under "Salmonella sepsis" PT
Salmonella sepsis recurrent	10066745	LLT	Salmonella sepsis if recurrent	Under "Salmonella sepsis" PT
Tuberculous infections	10044756	HLT	Any active TB Mycobacterium tuberculosis, any site, latent or active	

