APPENDIX M. OPPORTUNISTIC INFECTIONS

Potential opportunistic infections include, but are not limited to, the following:

- *Acinetobacter* infection
- Aspergillosis
- Blastomycosis, extrapulmonary
- Burkitt's lymphoma
- Candidiasis of esophagus, bronchi, trachea, or lungs
- Cervical cancer invasive
- Coccidioidomycosis, disseminated or extrapulmonary
- Cryptococcosis, extrapulmonary
- Cryptosporidiosis infection, chronic intestinal (>1 month duration)
- Cytomegalovirus disease (other than liver, spleen, or nodes)
- Hepatitis B and C
- Herpes simplex bronchitis, pneumonitis, or esophagitis
- Herpes simplex ulcers chronic (>1 month)
- Herpes zoster (Shingles) when 2 distinct episodes or more than 1 dermatome
- Histoplasmosis disseminated or extrapulmonary
- Human polyomavirus infection
- Isosporiasis, chronic intestinal (>1 month's duration)
- Kaposi's sarcoma
- Listeriosis
- Lymphoid interstitial pneumonia
- Lymphoma immunoblastic
- Lymphoma primary of brain
- *Mycobacterium avium* complex or *M. kansasii*, disseminated or extrapulmonary
Mycobacterium infections, other species or unidentified species, disseminated or extrapulmonary (eg, *M. haemophilum*, *M. fortuitum*, or *M. marinum*)
- *Mycobacterium* tuberculosis, any site, latent or active
- Nocardiosis
- *Pneumocystis jiroveci* infection
- Pneumonia, recurrent

- Polyomavirus (JC virus or BK virus)-associated nephropathy (including progressive multifocal leukoencephalopathy)
- *Salmonella* sepsis
- *Salmonella* septicemia, recurrent
- Shingles
- Toxoplasmosis of brain
- Any active tuberculosis
- Wasting secondary to human immunodeficiency virus (HIV)

Source: Modified from the Panel on Opportunistic Infections in HIV-Infected Adults and Adolescents. Guidelines for the prevention and treatment of opportunistic infections in HIV-infected adults and adolescents: recommendations from the Centers from Disease Control and Prevention, the National Institutes of Health, and the HIV Medicine Association of the Infectious Disease Society of America. Available at http://aidsinfo.nih.gov/contentfiles/lvguidelines/adult_oi.pdf.

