### 8.3.1.6. Opportunistic Infections

Opportunistic infections will be defined based on the following list of terms, derived from the preferred term (PT) or low level term (LLT) summarized in [Table 4](#). Food and Drug Administration (FDA) terms provided are from the Panel on Opportunistic Infections in HIV-Infected Adults and Adolescents.

Summaries will be presented by preferred term and previous double-blind treatment group.

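### SAP Table 4 captures non-disseminated herpes zoster only through the LLT Shingles, not its parent PT, and gives no rule for the episode/dermatome condition

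*SAP*

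**What the plan says.** SAP 8.3.1.6 states: "Opportunistic infections will be defined based on the following list of terms, derived from the preferred term (PT) or low level term (LLT") given in Table 4, with the summary presented by preferred term and previous double-blind group.

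Table 4 has three zoster rows:

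- Shingles, at LLT level, with the last column placing it under the PT Herpes zoster
- "Herpes zoster cutaneous disseminated", at PT level
- "Herpes zoster disseminated", at PT level

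All three are matched in the source-list column to the same entry: "Shingles when 2 distinct episodes or more than 1 dermatome". The PT Herpes zoster has no row. Neither SAP 8.3 nor 8.3.1.6 says how the episode or dermatome condition is to be checked.

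Protocol Appendix M, to which Protocol 7.1.6 refers for opportunistic infections, opens with "Potential opportunistic infections include, but are not limited to, the following". One of its bullets reads "Herpes zoster (Shingles) when 2 distinct episodes or more than 1 dermatome". A separate, later bullet reads simply Shingles, without a condition.

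**The concern.** A term list should send the same clinical event to the same place whichever word the site used. Here the PT is the stable unit, and the table searches below it, on one of the words that code to it. Appendix M puts Shingles in parentheses after Herpes zoster, so to the investigator they are one disease. An event coded to the PT Herpes zoster by any route other than the LLT Shingles is missed, although Herpes zoster is the protocol's leading term.

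Opportunistic infections are a protocol-defined event of special interest. Protocol 1.2.2.3.2 says that none were reported in the intravenous programme, so even a small number in this table would be noticed. The set that sites identify from Appendix M and the set that the SAP tabulates could also differ without explanation. The SAP introduction says that the SAP prevails over the protocol, and its Table 7 of changes does not mention this definition.

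**Working it through.** There is no stated figure to reproduce. The check is a count of rows and a reading of the rule against both Appendix M entries.

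**Row count in Table 4.** Zoster rows: 3 (1 LLT, 2 PTs). Rows for the PT Herpes zoster: 0. Rules in SAP 8.3 or 8.3.1.6 that apply the condition: 0.

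**Applying the rule literally.** This assumes that the PT Herpes zoster can be reached through at least one lower-level term other than Shingles. The table's own distinction between that LLT and its parent PT implies this.

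| Event | Coded to | In Table 4? | Meets the conditioned Appendix M entry? | Meets the unconditioned entry? |
|---|---|---|---|---|
| (a) One episode, one dermatome | LLT Shingles | Yes | No | Yes |
| (b) Same event as (a) | Another LLT under PT Herpes zoster | No | No | Yes, if the words are synonyms |
| (c) Two episodes, or several dermatomes without dissemination | LLT Shingles | Yes | Yes | Yes |
| (d) Same event as (c) | Another LLT under PT Herpes zoster | No | Yes | Yes, if the words are synonyms |
| (e) Disseminated zoster | Either disseminated PT | Yes | Yes, as Table 4 maps it | Yes |

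Three things follow.

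1. Rows (a) and (b), and rows (c) and (d), differ only in coding, yet are classified differently.
2. Row (d) is omitted although it qualifies under either Appendix M entry, so the gap does not depend on how the protocol's two entries are reconciled.
3. Table 4 matches neither entry in full. Under the conditioned entry it disagrees at (a) and (d); under the unconditioned entry, at (b) and (d).

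**Is LLT-level searching simply the table's convention?** Table 4 has 6 LLT rows: chronic herpes simplex skin ulcers, Shingles, lymphoid interstitial pneumonia, recurrent pneumonia, Salmonella septicemia and recurrent Salmonella sepsis. For both Salmonella rows the parent PT is also listed. For the simplex, interstitial pneumonia and recurrent pneumonia rows, the LLT is narrower than its parent and carries the needed qualifier (chronic, lymphoid, recurrent). Shingles does neither: its parent is absent, and the word says nothing about episodes or dermatomes.

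**Consequence in the outputs.** The opportunistic-infection table is by PT, so events entering through the LLT Shingles appear on a Herpes zoster line. The overall adverse event summary counts every event under that PT. The first line can therefore be smaller than the second under the same label.

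**Exposure.** If all of the approximately 360 planned patients completed 36 weeks, on-treatment exposure would be 360 × 36 × 7 / 365.25 = 248 patient-years. Turning that into cases needs a zoster rate, which the documents do not give.

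**The case against.** The best defence has four parts.

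- **The table is a proxy.** Other rows also carry clinical qualifiers with no rule, for example the one-month duration for cryptosporidiosis and isosporiasis. This stands as a description of Table 4 in general. It answers the missing condition better than it answers the missing parent PT.
- **Zoster is not captured through Shingles alone.** A reader might infer that it is. That is too strong: the two disseminated PTs count whatever the LLT, and they partly serve the limb on more than one dermatome. No term serves the limb on two distinct episodes.
- **Counting a single-dermatome case is not clearly an error.** A reader might call the search over-inclusive at row (a). The unconditioned Shingles bullet in Appendix M supports including that case, and the appendix list is open-ended. What stands is that the protocol's two entries disagree.
- **No case disappears.** SAP 8.3 summarises all adverse events by SOC and/or PT, lists every event and provides the mapping of dictionary terms. Protocol 7.1.6 separately routes infections of special interest to the sponsor's safety group. This stands in full and limits the point to one sub-table.

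None of this answers row (d), where a qualifying event is left out because of the term to which it was coded.

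**Conclusion.** The point holds in a narrow form. Outside the two disseminated PTs, entry to the opportunistic-infection table depends on the LLT to which a zoster event codes, and the episode/dermatome condition is printed but not applied. The stated rule can omit qualifying events, which is more than missing detail.

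The impact is one descriptive table. No test, primary result or overall adverse event count changes. It is tempting to put a number on the swing, or to say that zoster would dominate this table. The documents support neither: they give no rate for zoster or for the other listed terms, and the 248 patient-years assume full enrolment and no discontinuation. This is a cheap correction of low severity. It rests on Appendix M's equation of the two words and on zoster being codable to the PT by a term other than Shingles.

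**What to change.** - In Table 4, replace the LLT Shingles row by the PT Herpes zoster, and keep the two disseminated PTs.
- Reconcile the two Appendix M entries, so that the protocol states either one condition or none, and carry the result into SAP 8.3.1.6.
- Show all zoster in the opportunistic-infection table. If the condition is kept, add a line for cases that meet it on documented medical review of the listed cases.
- Record the change in SAP Table 7 if the resulting definition differs from the protocol.

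The cost is one table row, a sentence or two of text and review of a few cases. No new data collection is proposed; where the recorded detail does not settle episodes or dermatomes, the review should say so.

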#### 8.4. Deaths

If any patient dies during the study, a listing of deaths will be provided, and all relevant information will be discussed in the patient narrative included in the CSR.

#### 8.5. Clinical Laboratory Tests

Clinical laboratory tests (serum chemistry and hematology) will be performed prior to reslizumab administration at the time points detailed in Table 1 of the protocol. Clinical

laboratory tests will be performed using the central laboratory. Specific laboratory tests to be performed are provided in protocol section 7.4.1.

Summary statistics for laboratory tests will be presented at each scheduled visit. Actual values and changes from baseline to each visit will be summarized using descriptive statistics. Shifts (below, within, and above the normal range) from baseline to each visit will be summarized using patient counts and percentages. Shifts from baseline (Grade 0-4) will be provided for creatine phosphokinase (CPK) at each visit, based on the following grading scale:

- **Grade 0:** <1.25 x ULN
- **Grade 1:** 1.25 to 1.5 x ULN
- **Grade 2:** 1.6 to 3 x ULN
- **Grade 3:** 3.1 to 10 x ULN
- **Grade 4:** >10 x ULN

For CPK values  $\geq 3.1 \times \text{ULN}$  (Grade 3-4), investigators will collect additional information promptly from the patient related to symptoms associated with the elevation and any potential alternate causes. This supplemental data will be reported in the patient listings.

The incidence of potentially clinically significant abnormal values will be summarized for laboratory data using descriptive statistics with the criteria specified in [Table 5](#); criteria have been provided for adults and adolescents separately.

Summaries of potentially clinically significant laboratory values will include all relevant post-baseline values (including scheduled, unscheduled, and early termination visits). A post-baseline laboratory value will be considered potentially clinically significant only if it satisfies the specified criteria and is more extreme (farther from the limit) than the baseline value. Listings for potentially clinically significant laboratory data will be presented. If any patient has a positive pregnancy test, relevant information will be supplied in data listings.

A scatter plot will be provided for the baseline and maximum value for CPK.

**Table 5: Criteria for Potentially Clinically Significant Laboratory Values**

Test	Adults (≥18 years)		Adolescents (12 to <18 Years)		
	Criterion value	Change from baseline	Criterion value	Change from baseline	
Serum chemistry					
Alanine aminotransferase	≥3xULN	Increase >0	≥3xULN	Increase >0	
Aspartate aminotransferase	≥3xULN	Increase >0	≥3xULN	Increase >0	
Alkaline phosphatase	≥3xULN	Increase >0	≥3xULN	Increase >0	
Gamma-glutamyl transpeptidase	≥3xULN	Increase >0	≥3xULN	Increase >0	
Lactate dehydrogenase	≥3xULN	Increase >0	≥3xULN	Increase >0	
Blood urea nitrogen	≥10.71 mmol/L	Increase >0	≥10.71 mmol/L	Increase >0	
Creatinine	≥177 µmol/L	Increase >0	≥177 µmol/L	Increase >0	
Uric acid:	Men Women	≥625 µmol/L ≥506 µmol/L	Increase >0 Increase >0	≥625 µmol/L ≥506 µmol/L	Increase >0 Increase >0
Bilirubin (total)	≥34.2 µmol/L	Increase >0	≥34.2 µmol/L	Increase >0	
Creatine phosphokinase	Grade 3: 3.1 to 10 x ULN Grade 4: >10 x ULN	Increase >0	Grade 3: 3.1 to 10 x ULN Grade 4: >10 x ULN	Increase >0	
Hematology					
Hematocrit:	Men Women	<0.37 L/L <0.32 L/L	Decrease >0 Decrease >0	<0.30 L/L <0.30 L/L	Decrease >0 Decrease >0
Hemoglobin:	Men Women	≤115 g/L ≤95 g/L	Decrease >0 Decrease >0	≤100 g/L ≤100 g/L	Decrease >0 Decrease >0
White blood cell counts		≤3 x 10  /L ≥20 x 10  /L	Decrease >0 Increase >0	≤3 x 10  /L ≥20 x 10  /L	Decrease >0 Increase >0
Eosinophils		≥1.5 x 10  /L	Increase >0	≥1.5 x 10  /L	Increase >0
Absolute neutrophil counts		≤1 x 10  /L	Decrease >0	≤1 x 10  /L	Decrease >0
Platelet counts		≤75 x 10  /L ≥700 x 10  /L	Decrease >0 Increase >0	≤75 x 10  /L ≥700 x 10  /L	Decrease >0 Increase >0

ULN=upper limit of normal range.

If both the baseline and post-baseline values are beyond the same PCS limit, then the post-baseline value will be considered PCS only if it is more extreme (farther from the limit) than the baseline value. If the baseline value is beyond the low PCS limit and the post-baseline value is beyond the high PCS limit (or vice-versa), then the post-baseline value will be considered PCS

## 8.6. Physical Examinations

Physical examinations, including height and weight, will be performed at the time points detailed in Table 1 of the protocol.

A full physical examination (performed before spirometry) will include at a minimum the following organ systems: general appearance; head, eyes, ears, nose, and throat (HEENT); chest and lung; heart; abdomen; musculoskeletal; skin; lymph nodes; and neurological.

Shifts (normal and abnormal) from baseline to each visit will be summarized using patient counts and percentages for each category.

## 8.7. Vital Signs

Summary statistics for vital signs (blood pressure [BP] (systolic/diastolic), respiratory rate, body temperature, and pulse) will be measured at the time points detailed in Table 1 of the protocol. Actual values and changes from baseline to each visit will be summarized.

The incidence of potentially clinically significant vital signs will be summarized. Summaries of potentially clinically significant values will include all relevant post-baseline values (including scheduled, unscheduled, and early termination visits).

**Table 6** specifies the criteria for identifying vital signs as potentially clinically significant for adults and adolescents. In order to be identified as potentially clinically significant vital sign, the result would need to meet both identified conditions (ie, satisfies the specified criteria and results in a change from baseline of at least the magnitude specified). A listing for potentially clinically significant vital signs will be presented.

**Table 6: Criteria for Potentially Clinically Significant Vital Signs**

	Adults (≥18 years)		Adolescents (12 to <18 Years)	
Vital Sign	Criterion value	Change from baseline	Criterion value	Change from baseline
Heart rate	>100 bpm	Increase of ≥30	>100 bpm	Increase of ≥30
	<50 bpm	Decrease of ≥30	<60 bpm	Decrease of ≥30
Systolic BP	>160 mmHg	Increase of ≥30	>130 mmHg	Increase of ≥30
	<90 mmHg	Decrease of ≥30	<90 mmHg	Decrease of ≥30
Diastolic BP	>100 mmHg	Increase of ≥12	>85 mmHg	Increase of ≥12
	<50 mmHg	Decrease of ≥12	<55 mmHg	Decrease of ≥12
Respiratory rate	>24 breaths/min	Increase of ≥10	>20 breaths/min	Increase of ≥10
	<6 breaths/min	Not applicable	<10 breaths/min	Not applicable
Temperature	>38.1°C	Increase of ≥1.1	>38.1°C	Increase of ≥1.1
	<35.8°C	Not applicable	<35.8°C	Not applicable

